4.0 Sample Size and Power

This is a Phase 1 study first in humans with four dosing cohorts and no formal sample size calculations based on testing a statistical hypothesis were constructed. Sample sizes are consistent with this type of early phase study. Dosing groups of ten participants each, eight participants assigned the active group and two assigned to the control group, for each cohort are practical and provide sufficient information for a total sample size of 40 for a Phase 1 trial primarily designed to assess safety.

The dosing groups of eight participants in the active group has a probability of at least one subject experiencing an event of toxicity ranges from 0.728 to 0.996 assuming true event rates are between 0.15 and 0.5.

Additionally, if no events are observed in each scenario described above, the upper bound of an exact 95% confidence interval for the true proportion is 0.369.

5.0 Analysis Populations

Full Analysis Set (FAS)/Intention-To-Treat population (ITT)

An intent-to-treat population will consist of all subjects randomized and will be analyzed as randomized.

Safety population (Safety)

All subjects who received study product will be included in the safety population and analyzed as treated.

Per-Protocol population (PP)

The Per-protocol population will consist of all subjects in the ITT population who were free from major protocol violations. Patients will be included in the analysis according to the treatment group they are randomized to.

Pharmacokinetics (PK) population

The PK population will consist of all subjects who complete ADM03820 injection and have sufficient evaluable PK samples for the estimation of PK parameters. Subjects in the PK population will be analyzed in the dose cohort and treatment group corresponding to the study drug that they have received.

Protocol deviations

Protocol deviation data will be captured in the clinical trial management system. Extracts of all protocol deviations will be reviewed periodically and prior to any interim or final analyses. All protocol deviations and the exclusion of participants from analysis sets will be identified prior to unblinding through clinical review and input provided by the sponsor using supportive participant listings provided by the ICON GPHS statistician based upon data recorded in the clinical trial management system.

Further, deviations from the protocol will be classified as major or minor. Classification of major and minor protocol deviations is determined prior to participant enrollment and is outlined in detail in the protocol deviation criteria documentation managed by the clinical trial management team.

6.0 Statistical Considerations and Analysis

Derived Variables

The below table provides the list of derived variables for demographic and baseline characteristics, various duration derivations, baseline derivation and other important derivations applicable for this study.

Table 3: Derived Variables

Variables	Formula						
Demographic and Baseline Characteristics							
Age at informed consent (in years)	Integer ((date of informed consent – date of birth + 1) / 365.25)						
Body Mass Index	Weight (kg) / [height (m)] ²						
Derivation of Durations							
Study day at any visit	Date of interest – date of first dose of vaccine. One day is added if the difference is ≥ 0.						
Duration of any events	End date of event – start date of event + 1						
Baseline Derivations							
Laboratory results/vital signs baseline The baseline value is defined as the last observation prior to or on the date of dosing							
Derivations of Changes	Derivations of Changes						
Change from baseline	Post baseline value – baseline						
Change from previous visit	Current value – previous value						
Change after dosing from before dosing	Value after dose – value before dose						
Pharmacokinetic Parameters (PK) (Plasma/Serum)							

Variables	Formula
C _{max}	Maximum observed concentration, occurring at time T _{max} .
T _{max}	Time of maximum observed concentration. For non-steady-state data, the entire curve is considered. If the maximum observed concentration is not unique, then the first maximum is used.
AUC _(0-t)	Area under the concentration time-curve from the time of dosing to the time of the last measurable (positive) concentration
λz	First-order rate constant associated with the terminal (log-linear) portion of the curve, estimated by linear regression of time vs. log concentration during steady-state elimination
AUC _(0-∞)	Area under the concentration time-curve from time of dosing extrapolated to infinity, based on the last observed concentration or last predicted concentration defined as $AUC_{(0-t)} + (C_{(0-t)}/\lambda_z)$
t _{1/2}	Terminal half-life defined as ln(2)/ λ_z as measured during steady-state
CL	Total body clearance for extravascular administration defined as Dose/ AUC _(0-∞)
Vz	Volume of distribution based on the terminal phase. For non-steady-state data defined as Dose/[λ_z (AUC _(0-∞))]

Handling of missing data and outliers

All attempts will be made to collect all data per protocol. No imputations will be conducted for missing values. Outliers identified during the PK analysis will be discussed in the analysis report.

Missing data analysis methods

Imputation rules for missing or partial adverse event start/stop dates

- If the AE start date day is missing (month and year provided) then set the date to the first of the
 month unless the month and year are the same as the first dose of study drug. In this case, set the
 date to the date of first dose.
- If the AE start date month is missing (year is provided) then set the month and day to January 1, unless the year is the same as the year of the first dose. In this case, set the date to the date of first dose.
- If the AE end date day is missing (month and year provided) then set the date to the last day of the month.
- If the AE end date month is missing (year is provided) then set the date to December 31.

• If the year of the AE start date or AE end date are missing, then a query to the site must be made to gather additional information. If the end date and start date are both missing, then no imputation will be done. If the stat date remains missing but the end date is before first dose date, then the AE will be considered before treatment. If the end date is after the first dose, then the AE will be considered to have been treatment emergent.

Imputation rules for missing or partial medication start/stop dates

Start Date:

- If only day is missing, use the first day of the month.
- If day and month are missing, use the first day of the year.
- If day, month, and year are missing use the first day of the year with the same year as the first dose.

End Date:

- If only day is missing, use the last day of the month.
- If day and month are missing, use the last day of the year.
- If day, month, and year are missing assign 'continuing' status to the stop date.

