7.3. Vital Signs

Vital sign assessments including systolic and diastolic blood pressure (BP) [measured after sitting for at least 10 minutes], heart rate (HR), respiratory rate, and oral temperature will be performed at each in-clinic study visit. Vital signs that are thought to be aberrant due to an error in measurement may be repeated. During screening and follow-up, a measurement that is a Grade 1 (as referenced in Appendix B by CTCAE version 5.0) may be repeated once if the PI believes a transient condition led to the aberrant value.

Vital signs obtained at screening will serve as baseline values for the subject. Grade 1 values are allowable unless deemed clinically significant by the study investigator.

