8.2. Visit 2: Baseline / Day of Dosing (Day 1)

Subjects meeting inclusion/exclusion criteria will be admitted to the clinical unit the day of injection and the following procedures will be performed prior to the study drug administration:

Prior to Dosing

- Review inclusion/exclusion to confirm eligibility
- Review CDC fact sheet on prevention of COVID-19 with subject
- Review and update concomitant medications and medical history
- Obtain vital signs
- Perform abbreviated physical examination with focused assessment for the presence of the following in order to detect signs of a hypersensitivity reaction:
 - General appearance including alertness, diaphoresis, chills, and any difficulty breathing.

- HEENT (confirm no swelling of lips/tongue/uvula)
- Chest (confirm no stridor or wheezing)
- Heart (assess regularity of rhythm)
- Skin (confirm no hives, examine for any eruptions)
- Joints (confirm no swelling, warmth, or tenderness)
- Perform Breathalyzer test or blood/saliva alcohol test to detect recent alcohol use
- Obtain urine sample for toxicology
- For women, a urine Hcg test will be done. The results must be confirmed to be negative before dosing
- Obtain blood samples for baseline serum PK and future use (for subjects who consent)
- Obtain blood sample for ADA
- Obtain blood sample for MN
- Obtain blood sample for RT-PCR testing
- Obtain blood sample for hypersensitivity panel
- Randomize the subject
- Obtain study product from the pharmacy
- Counsel both men and women of child-bearing potential on the avoidance of pregnancy

During Dosing

- Study product should be injected into the gluteus medius (see Appendix C). First divide the buttock in half from top to bottom and then in half from side to side. The injection should be given in the upper outer quarter.
- A study physician should be present at the time of study drug administration and the subject will be under direct observation during at least the initial 30 minutes after the injection by clinical study staff. The study staff should observe the subject closely for signs and symptoms of anaphylaxis and anaphylactoid type reactions. Should an adverse reaction of this type occur, the subject will be treated using the standard protocol at the site
- Obtain vital signs (blood pressure, heart rate, respiratory rate, and oral temperature) 15 (±3) minutes after the injection is completed.

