11.3.3.2. Additional Safety Analyses

Vital signs, physical examinations, and clinical laboratory values, including change from baseline, will be summarized by dose cohort and control group.

Descriptive summary statistics for laboratory data at admission (baseline value) and each applicable post-dose visit, including change from the baseline value, will be calculated. Descriptive summary statistics for vital signs at screening (baseline value) and each applicable post-dose visit, including change from the baseline value, will be calculated. Shift tables, showing individual subject changes from baseline will be presented for laboratory parameters using toxicity grading. Subjects with Graded values of vital sign and laboratory parameters will be identified in listings.

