8. A urine dipstick will be done to evaluate for presence of protein, glucose or blood in urine. If dipstick is abnormal, a complete urinalysis with microscopic will be performed.

9. A 12-lead ECG will be performed during screening and post dose performed 30 minutes (±10 minutes) after completion of dosing.

10. Viral Serology includes HIV, HBsAg and antibody to HCV.

11. PK samples will be taken at the following times: pre-dose, 2, 4, 8, and 24 hours post injection and on days 2, 3, 4, 8, 15, 30, 45, 60, 90, 120, 150, 180, and 365 for all cohorts

12. Serum from subjects who give consent for future use samples will be collected at 2 hr and 4 hr post dose and on days 2, 8, and 30

13. Vital signs (sitting for at least 10 minutes) will be checked just before injection and every visit.

14. The subject will be under direct observation during at least the initial 30 minutes of dosing. A physical examination will be performed at approximately 30 minutes post injection or in response to subject symptoms which will include the following: General appearance including alertness, diaphoresis, chills, and any difficulty breathing, HEENT, Chest, Heart, Skin and Joints

15. Draw prior to dosing at baseline

16. The Hypersensitivity Panel includes cytokine and complement panels, IgE, and tryptase. Draw 14ml prior to dosing. If a subject develops anaphylaxis or anaphylactoid reaction, an additional 10 mL sample will be drawn during the event and another will be drawn after the event

Protocol: ADM03820-001

Version 6.0 July 14, 2022

- 17. Subjects in all cohorts will receive RT-PCR testing at screening, Day 1 prior to dosing, and at presentation of symptoms.
- 18. SARS-CoV-2 antibodies will only be tested in Cohorts 1-4 (Not applicable for Cohort 5).

19. TC visits will be conducted for only Cohorts 1-4 (Not applicable for Cohort 5).

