7.0 Statistical Methods

General statistical conventions

All statistical procedures will be completed using SAS version 9.4 (or higher), R version 4.0.0 (or higher), or Phoenix WinNonLin 8.3.1 (or higher).

Unless otherwise stated, all statistical testing will be two-sided and will be performed using a significance (alpha) of 0.05. Two-sided 95% confidence intervals (CI) will be provided when relevant.

Continuous variables will be summarized using descriptive statistics, including number of subjects (n), mean, median, standard deviation (SD), interquartile ranges (IQR), minimum, and maximum.

For categorical variables, summaries will include counts of subjects and percentages. Percentages will be rounded to one decimal place.

For summary purposes, baseline will be defined as the last available pre-dose value. All summaries will be presented by treatment group, unless otherwise specified.

All subject data, including those derived, will be presented in individual subject data listings. Unless otherwise stated, unscheduled visit results will be included in date/time chronological order, within patient listings only. All listings will be sorted by subject ID, date/time and visit. The treatment group will be stated on each listing. Unless otherwise stated, data listings will be based on FAS.

Unscheduled data points will not be used in any summary tables separated by visit but will be presented in each listing as appropriate.

Subject disposition

Subject disposition information will be summarized by dosing cohort, treatment group and overall. The number and percentage of subjects who are enrolled, who complete the study, and who withdraw early from the study will be presented.

The primary reasons for early withdrawal will also be tabulated, including withdrawal by subject, physician decision, lost to follow-up, major protocol deviation or other.

The number of subjects enrolled will be used as the denominator for the percentage calculation. Subject disposition will be listed.

The number and percent of subjects in each analysis set will also be tabulated. A listing of each subject excluded from an analysis population will be listed as well as the reason why they were excluded from the population.

Treatment Misallocations: if a subject is

- Randomized but withdrawn prior to dosing, then they will be replaced and will not be included in any analysis.
- Randomized but receive incorrect treatment, they will be reported under the treatment they actually

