8.0 Changes to Planned Analysis from Study Protocol

Added per-protocol population in protocol section 11.3.1.

Resilience Government Services, ADM03820-001

BST1302-SOP-T01/v1.0/2020 Page 25 of 26

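### Vital-sign baseline has three conflicting definitions, and SAP Table 3 taken literally selects a reading about 6 hours after dosing

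*SAP*

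**What the plan says.** Three rules apply to the vital-sign baseline.

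- **SAP 6.0, Table 3**, in the row covering laboratory results and vital signs: "The baseline value is defined as the last observation prior to or on the date of dosing".
- **SAP 7.0**, general conventions: "For summary purposes, baseline will be defined as the last available pre-dose value".
- **Protocol 7.3**: "Vital signs obtained at screening will serve as baseline values for the subject". Protocol 11.3.3.2 repeats this for the analysis: "Descriptive summary statistics for vital signs at screening (baseline value) and each applicable post-dose visit".

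SAP 8.0, which records changes from the protocol analysis, has one entry: "Added per-protocol population in protocol section 11.3.1". It does not mention baseline.

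Two related provisions matter. SAP 8.7.3 summarises vital signs by visit or time point and defines the visit value as an average over every reading of the parameter. For laboratory data, protocol 11.3.3.2 places the baseline on admission: "Descriptive summary statistics for laboratory data at admission (baseline value) and each applicable post-dose visit".

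**The concern.** The three rules would be harmless if they picked the same reading, but the schedule makes them pick different ones. Vital signs are taken at screening, again just before injection, and repeatedly afterwards on the same calendar date. Table 3 is the SAP's derivation table and its row names vital signs, so a programmer could reasonably treat it as the specific rule and SAP 7.0 as the general one. Followed that way, baseline becomes a post-dose measurement.

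Change from baseline in vital signs is part of the third of three primary endpoints (protocol 3.2.1). A post-dose baseline subtracts any effect still present at that moment from every later visit. It also leaves the Day 1 post-dose readings with no meaningful change from baseline. Even if SAP 7.0 governs, the SAP still departs from the protocol's screening baseline without saying so.

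**Working it through.** The plan states no figure for this point. The check applies each rule to the schedule and then works out the difference algebraically.

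**Day 1 readings**

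- Pre-dose: protocol 8.2 lists a set before dosing, and Appendix A, footnote 13, says "Vital signs (sitting for at least 10 minutes) will be checked just before injection and every visit".
- First post-dose set (protocol 8.2, During Dosing): "15 (±3) minutes after the injection is completed".
- Hourly for 2 hours (protocol 8.2, Post Dosing): 1 h and 2 h.
- Every 2 hours over the following 4 hours: 4 h and 6 h, because 2 + 4 = 6.

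This gives 6 sets, 5 of them post-dose. The next scheduled reading is at discharge on Day 2.

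**Reading selected by each rule**

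| Rule | Reading taken as baseline |
|---|---|
| Protocol 7.3 and 11.3.3.2 | Screening (Day -14 to -2) |
| SAP 7.0 | Day 1, just before injection |
| SAP Table 3, literal | Day 1, 6 h after injection |

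The 6-hour result holds for injections completed before about 18:00. For later injections the literal rule takes the last scheduled reading before midnight: 4 h for 18:00 to 19:59, 2 h for 20:00 to 21:59, and 1 h for 22:00 to 22:59. All are still post-dose. Extra readings at the investigator's discretion could also move the selected time.

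**Effect on change from baseline**

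Let S be the screening value, P the pre-dose value, P + d the 6-hour value, and P + rd the value at a later visit, where r is the share of the shift that remains. Then:

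- Table 3: (P + rd) - (P + d) = (r - 1)d
- SAP 7.0: (P + rd) - P = rd
- Protocol: (P + rd) - S = rd + (P - S)
- Table 3 minus SAP 7.0: (r - 1)d - rd = -d, whatever r is

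The documents give no value for d, so a range is assumed:

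| d | r | Table 3 | SAP 7.0 |
|---|---|---|---|
| 5 | 0 | -5 | 0 |
| 5 | 1 | 0 | 5 |
| 10 | 0 | -10 | 0 |
| 10 | 0.5 | -5 | 5 |
| 10 | 1 | 0 | 10 |
| 15 | 0 | -15 | 0 |
| 15 | 1 | 0 | 15 |

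A resolved shift appears as a change of opposite sign, and a persistent shift appears as no change. The offset applies at 13 later in-clinic visits: Days 2, 3, 4, 8, 15, 30, 45, 60, 90, 120, 150, 180 and 365. At 6 h itself the Table 3 change is 0 for every subject by construction. Table 3 also defines change as post-baseline minus baseline, so none of the 5 Day 1 post-dose sets counts as post-baseline.

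The post-dose reading would be selected in all 50 subjects, but only the 5 × 8 = 40 on active can carry a drug effect. A shift common to both arms cancels in an active-placebo contrast; a drug-specific shift does not.

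**Averaging in SAP 8.7.3**

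If the average is taken over the whole of Day 1, an effect d seen at one of six readings contributes d/6 to the visit value. This is only one possible reading of the text.

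**Laboratory baseline**

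Protocol 7.5.2, Table 2 and Appendix A schedule no safety blood sample on Day 1; Appendix A has only a urine dipstick. For blood tests, Table 3 and SAP 7.0 therefore both fall back to screening, so those baselines do not become post-dose. The protocol's reference to admission has no scheduled safety blood sample behind it.

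**The case against.** The best reply is that the two SAP rules can be read together. Every pre-dose value also falls on or before the dosing date, so SAP 7.0 can be seen as supplying the clock-time limit that Table 3 omits. Table 3 itself has a separate variable for the value after dosing minus the value before, and baseline ordinarily means before treatment. On that view the 6-hour reading requires ignoring SAP 7.0, and the only real conflict is screening against Day 1 pre-dose, both untreated.

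This is a sensible reading, and a careful programmer might adopt it. But the SAP states no precedence, Table 3 is the rule that names vital signs, and its literal output is post-dose. The after-minus-before variable does not define baseline. The undeclared departure from the protocol remains on any reading.

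Several limits do stand:

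- d is assumed. If nothing remains at 6 h, for example after an effect seen only at 15 minutes, later visits are unbiased.
- Raw visit values and subject listings do not depend on baseline, adverse events are recorded and graded separately, and no tests are planned on safety endpoints.
- The SAP 8.7.3 average can be read as covering repeats at one time point. The table templates are in a separate document and may already specify nominal times.
- The laboratory point changes no SAP-based blood-test output.

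**Conclusion.** The concern holds and should be fixed. The vital-sign baseline is defined in three ways that select three different readings for a subject on schedule, and the derivation rule that names vital signs selects a post-dose value when followed as written. The protocol-to-SAP departure is not declared.

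Relative to SAP 7.0, the error is exactly -d at each of the 13 later visits, where d is whatever shift from pre-dose exists at the selected reading. That size rests on an assumed d and on the literal reading of Table 3. It affects the descriptive change-from-baseline summaries in one of the three primary endpoints. It does not affect the adverse-event or serious-adverse-event endpoints, the listings or the halting rules, so detection of acute safety events does not depend on it. The averaging and laboratory points are secondary matters of wording.

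**What to change.** - **SAP Table 3:** define baseline as the last non-missing value before the date and time of injection. For vital signs this is the Day 1 pre-injection set; for blood tests it is the screening value.
- **SAP 7.0:** use the same wording, so that only one rule exists.
- **Protocol 7.3 and 11.3.3.2:** align the vital-sign and laboratory baselines with that rule, or list the departure in SAP 8.0.
- **SAP 8.7.3:** summarise Day 1 by nominal time point (pre-dose, 15 min, 1, 2, 4 and 6 h), and average only repeat readings at the same time point.

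The cost is wording in four places in the SAP and, unless the table templates already include them, a few extra rows in the vital-sign table. If the protocol text is aligned instead of listing the departure, that is an added protocol edit. No new data are needed, because the pre-injection set is already scheduled.

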3.2.2. Secondary Endpoints

- The assessment of C_{max} , T_{max} and $AUC_{(0-t)}$ for total antibodies of ADM03820 as measured by enzyme-linked immunosorbent assay (ELISA) for samples from Cohorts 1 and 2. The assessment of C_{max} , T_{max} and $AUC_{(0-t)}$ for each of the monoclonal antibodies of ADM03820 as measured by enzyme-linked immunosorbent assay (ELISA) for samples from Cohort 3, Cohort 4, and Cohort 5.
 - Pharmacokinetic samples will be tested by ELISA at pre-dose, 2, 4, 8, and 24 hours post dose, and on Days 3, 4, 8, 15, 30, 45, 60, 90, 120, 150, 180, and 365 for all cohorts
 - Samples will be tested by Microneutralization at pre-dose and Days 2, 15, 30, 60, 90, 120, 150, and 180 for all cohorts
- Samples will be tested by Electrochemiluminescence Assay (ECLA) to evaluate presence of anti-drug antibodies (ADA) collected for all cohorts.
 - ADA samples will be tested at pre-dose, and Day 15, 30, 45, 60, 90, 120, 150, 180, 365 for all cohorts
- Incidence of the first case of SARS-SoV-2 RT-PCR positive symptomatic illness occurring after dosing through Day 365
- Incidence of SARS-CoV-2 RT-PCR positive severe or critical symptomatic illness occurring after dosing through Day 365
- Incidence of COVID-19 related Emergency Department visits occurring after dosing through Day 365

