5.3.4. Handling of Withdrawals

Subjects who are withdrawn prior to dosing must be replaced.

Following dosing, one subject per cohort may withdraw prior to the completion of Visit 11 (day 60) or was noncompliant with all PK draws through Visit 6 (day 4) without being replaced.

If 4 or more subjects withdraw, are lost to follow up or terminate prior to Day 8 within a cohort, at least one of those subjects need to be replaced to ensure that data for at least 7 subjects are available for review.

If 4 or more subjects withdraw, are lost to follow up or terminate on or after Day 8 but prior to Day 60 or are not compliant with all PK draws through Day 15 within a cohort, they should be replaced.

If more than 4 subjects withdraw, are lost to follow up or terminate following the Day 8 SRC review of safety data within a cohort, the site will attempt to replace those subjects in that dose group at the time of the next planned cohort.

All replaced subjects will be assigned to the same treatment assignment as the subject they are replacing. This will be documented in the source documents and eCRFs.

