11.2. Planned Interim Analyses

There are several blinded interim analyses planned for this study. A blinded interim analysis is planned to analyze all PK samples through Day 30 for all subjects in Cohorts 1 and 2. A second blinded interim analysis is planned to analyze all PK samples after all subjects in cohorts 1-3 complete Day 60. A third interim analysis is planned to analyze safety and PK data after all subjects in cohort 5 complete Day 60.

There is also an interim clinical study report (CSR) planned after subjects in Cohorts 1 through 4 complete Day 90.

Stopping criteria are for safety and are defined in section 9.5. No adjustments for multiplicity will be made at these interim analyses.

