11.3.4. PK Analysis Plan

PK parameters will be estimated for total antibodies of ADM03820 as measured by enzymelinked immunosorbent assay (ELISA) for samples from Cohorts 1 and 2. PK parameters for each of the monoclonal antibodies of ADM03820 as measured by enzyme-linked immunosorbent assay (ELISA) for samples from Cohort 3 and 4 using noncompartmental methods in WinNonlin or a similar software package. Parameters will be estimated by dose cohort. Summary statistics will include the mean, median, coefficient of variation, and range. When evaluable, estimated PK parameters will include:

- AUC_(0-t): Area under the concentration time-curve to the last concentration above the lower limit of quantitation
- C_{max}: Maximum observed concentration
- T_{max}: Time of maximum observed concentration
- Kel: Elimination rate constant
- $AUC_{(0-\infty)}$: Area under the concentration time-curve extrapolated to infinity
- t_{1/2}: Terminal elimination half-life
- CL: Total clearance
- V_z: Volume of distribution

Additionally, multi-compartmental models will be considered based on inspection of concentration-time curves. If models are fit, base models will assume first-order elimination from the central compartment, and models will be parameterized in terms of clearance, volume of distribution and inter-compartmental rates. Standard objective goodness of fit measures will be used to determine the final model.

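### AUC(0-t) ends at each subject's own last measurable sample and no AUC over a common interval is planned, so early leavers and an uncut interim 2 can distort cohort comparisons

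*SAP*

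**What the plan says.** SAP Table 3 (section 6.0) defines AUC(0-t) as "Area under the concentration time-curve from the time of dosing to the time of the last measurable (positive) concentration". Protocol 11.3.4 and SAP 8.8.2 agree in substance; the protocol has "Area under the concentration time-curve to the last concentration above the lower limit of quantitation". The secondary endpoints (Protocol 3.2.2, repeated in the SAP) are Cmax, Tmax and AUC(0-t). They are assessed "for total antibodies of ADM03820 as measured by enzyme-linked immunosorbent assay (ELISA) for samples from Cohorts 1 and 2", and for each monoclonal antibody separately in Cohorts 3, 4 and 5. AUC to infinity is estimated when evaluable but is not a listed endpoint.

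Sampling times are common to the whole study: pre-dose, 2, 4, 8 and 24 hours, then "Days 3, 4, 8, 15, 30, 45, 60, 90, 120, 150, 180, and 365 for all cohorts". Parameters are estimated by dose cohort and summarised by mean, median, coefficient of variation and range. Missing values are not imputed. The PK population needs sufficient evaluable samples, with no number or minimum follow-up given.

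On the interims, Protocol 11.2 says that the first will "analyze all PK samples through Day 30 for all subjects in Cohorts 1 and 2". For the second it says: "A second blinded interim analysis is planned to analyze all PK samples after all subjects in cohorts 1-3 complete Day 60". SAP Table 4 gives only Day 30 and Day 60 for these two.

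**The concern.** An area under the curve can be compared between subjects only if it covers the same stretch of time, or if what lies beyond the last sample is negligible. Here the upper limit is whatever each subject's record happens to reach. Two subjects with the same kinetics get different AUC(0-t) if one stops giving blood at Day 60 and the other at Day 365, and both enter the same cohort mean. The antibody carries a mutation intended to lengthen its half-life (Protocol 2.1.3), so the later part of the curve may carry substantial area.

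At interim 2 the same thing could happen to whole cohorts. Dosing is sequential, and the protocol's wording sets when the analysis may start, not where the data stop. Cohorts dosed earlier could therefore bring later samples.

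What is at stake is descriptive: apparent differences between doses or products within the same analyte. These are Cohort 1 against 2 (total antibody, 150 and 300 mg) and, at the end, Cohorts 3, 4 and 5 (single antibodies, 300 and 600 mg, with 50 or 100 mg/mL product). No PK hypothesis test depends on it.

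**Working it through.** **The plan's own figures.** None concerns AUC. The sample size figures in Protocol 11.1 reproduce (1 - 0.85^8 = 0.728; 1 - 0.5^8 = 0.996; 1 - 0.025^(1/8) = 0.369) but do not bear on this point. The PK schedule does: 4 draws on Day 1 plus 13 later make 17, and 17 x 6 mL = 102 mL, which matches Protocol Table 2. There is one schedule, to Day 365, for all cohorts.

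**Model (assumed).** One compartment, with first-order absorption ka of 0.2-0.4 per day and half-life of 21-90 days. The documents give neither. With k = ln 2 / half-life, the fraction of AUC(0-inf) accrued by t days is

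F(t) = [(1 - e^(-kt))/k - (1 - e^(-ka t))/ka] / (1/k - 1/ka).

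Example with half-life 60 days and ka 0.2: 1/k = 86.56 and 1/ka = 5. F(60) = (43.28 - 5.00)/81.56 = 0.469. F(365) = (85.28 - 5.00)/81.56 = 0.984. The ratio is 0.477.

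| Half-life (days) | F(60)/F(365) | F(60)/F(90) |
|---|---|---|
| 21 | 0.835-0.850 | 0.889-0.900 |
| 30 | 0.718-0.735 | 0.835-0.847 |
| 60 | 0.477-0.493 | 0.751-0.763 |
| 90 | 0.368-0.381 | 0.718-0.730 |

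Counting Day 60 as 59 days after a Day 1 dose changes the results below by at most about 0.1 point (final) and 0.5 point (interim).

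**Final analysis.** There are 8 actives with identical PK, and m of them have a last sample at Day 60. With r = F(60)/F(365), the fall in the cohort mean is m(1 - r)/8. For m = 1 the added coefficient of variation is [(1 - r)/sqrt(8)] / [(7 + r)/8].

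| Half-life (days) | One leaver | Two leavers | Added CV, one leaver |
|---|---|---|---|
| 21 | 1.9-2.1% | 3.8-4.1% | 5-6% |
| 30 | 3.3-3.5% | 6.6-7.1% | 9-10% |
| 60 | 6.3-6.5% | 12.7-13.1% | 19-20% |
| 90 | 7.7-7.9% | 15.5-15.8% | 24% |

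A single subject whose last sample is at Day 180 lowers the mean by 0-3% over the same range.

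**Interim 2.** A cohort ending at Day 60 against one that includes Day 90, with identical PK, is lower by 1 - F(60)/F(90): 10-11% (21 days), 15-17% (30 days), 24-25% (60 days) and 27-28% (90 days). If Cohort 2 were the shorter one and exposure truly doubled from 150 to 300 mg, the Cohort 2 to Cohort 1 ratio would read 2 x 0.718 to 2 x 0.900, that is 1.44 to 1.80.

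**When that can happen.** The protocol's minimum spacing is a 48 h sentinel gap, then 4 h between subjects, then a Day 8 review of at least 7 subjects. Per cohort that is 48 + 4 x 4 = 64 h (7 dosed) or 48 + 7 x 4 = 76 h (all 10), plus 7 days. Two cohorts give 2 x (2.67 + 7) = 19.3 days or 2 x (3.17 + 7) = 20.3 days from Cohort 1 to Cohort 3. At that spacing Cohort 1 is near Day 80 when Cohort 3 reaches Day 60, so its Day 90 sample does not exist yet. The effect needs a gap of about 30 days. For Cohort 1 against 2 it also needs Cohort 2 to be less than about 30 days ahead of Cohort 3.

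**The case against.** AUC to the last quantifiable sample is a standard noncompartmental parameter, and much in the plan softens the problem. The PK population definition can exclude poorly sampled subjects. The early termination visit includes a PK draw, and leavers are followed where possible. Medians and individual listings will show an odd value. AUC(0-inf) is also planned. These points reduce the effect but do not remove it. The inclusion rule has no number, an early termination draw still ends the curve on the day of leaving, and AUC(0-inf) is neither a listed endpoint nor subject to an extrapolation limit.

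Several stronger readings are tempting but not supported:

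- **Cohorts have different PK follow-up by design.** They do not. Cohort 5's shorter follow-up drops only the Day 450 and 540 telephone visits, which have no PK draw.
- **Cohorts are averaged together.** Estimation is by dose cohort. SAP 8.6.5 speaks of treatment groups without saying how the three 300 mg cohorts are treated, but that is not a stated plan to pool.
- **Three leavers per cohort go unreplaced.** This takes one rule alone ("If 4 or more subjects withdraw, are lost to follow up or terminate on or after Day 8 but prior to Day 60"). Protocol 5.3.4 also allows one per cohort before Day 60, and 9.6.4 uses more than two after the Day 8 review. These passages need reconciling. They also count placebo subjects, who have no AUC.
- **Interim AUC feeds dose or phase 2 decisions.** Escalation and the step before phase 2 rest on Day 8 safety reviews. Nothing links them to AUC.
- **Shortening of t at low concentrations is an artefact.** It is largely a true feature of low exposure.
- **Interim 2 is certainly uncut.** SAP Table 4 can be read as a Day 60 cut. Cohort 3 also measures a different analyte from Cohorts 1 and 2.

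**Conclusion.** The point holds as a gap in comparability, not as an invalid endpoint. AUC(0-t) has no common upper limit and no common-window AUC stands beside it. In the final analysis the distortion comes only from subjects with early last samples. Per Day 60 leaver among 8 actives it is about 2% of the cohort mean at a 21-day half-life and 8% at 90 days; for two leavers it is about 4-16%. At interim 2 it could reach 10-28%, but only if dosing gaps were about 30 days or more and the data were not cut at Day 60. All sizes rest on an assumed one-compartment model, half-life and absorption rate, and the interim figure also on dosing dates that the documents do not give. It would be too strong to say that most of the area lies after Day 60: the model puts that share at 15-17% for a 21-day half-life and 64-66% for 90 days (1 - F(60), with F(60) = 0.835-0.850 and 0.345-0.358). This is a cheap improvement that changes no sample size or error rate.

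**What to change.** In SAP Table 3 and SAP 8.8.2:

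1. Keep AUC(0-t) as the specified secondary endpoint and report it with each subject's t.
2. Add partial AUCs over common windows: 0-30 days for interim 1, 0-60 days for interims 2 and 3, and 0-180 and 0-365 days for the final analysis. Compute each when sampling covers the window (the nominal visit's sample taken within its visit window) or when the concentration has already fallen below quantitation, and state how the remaining area is then counted.
3. Use the partial AUCs for comparisons between cohorts and doses within the same analyte.
4. State that interim 2 PK data are cut at Day 60 in all cohorts, if that analysis is still to be run or re-reported. The SAP is dated September 2023 and describes itself as for the final analysis, so this step may no longer be needed.

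The cost is SAP wording and a few partial-area settings in the PK software, with no new samples or visits. The drawback is that subjects without coverage drop out of the longer windows, which become completer summaries. Showing the number contributing to each window, beside AUC(0-t) for everyone, keeps that visible.
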